## **Recruitment period**

Recruitment for this study is anticipated to take approximately 4-6 weeks.

## **RECRUITMENT PROCEDURE**

All patients who meet eligibility criteria electing to undergo treatment with BTX-A will be offered this study. All patients interested will be provided with a written consent. Those who agree to participate, informed consent will be obtained and the participant will proceed into the Baseline Exam.

## **Randomization Procedure**

Upon completion of the Baseline Visit and eligibility of the participant is confirmed, their randomization assignment will be obtained from the computer-generated randomization table.

## **TREATMENT**

For each patient, one half of the forehead, divided from the contralateral side by an imaginary vertical line through the dorsum of the nose, will be treated with a thick layer of topical 2.5% lidocaine/2.5 % prilocaine cream (Impax Laboratories, LLC), while the other will be treated with 41% petrolatum ointment. After, 30 minutes, the ointment will be wiped away and the forehead will be cleaned with an alcohol swab and allowed to. Botulinum toxin type A (Botox, Allergan Pharmaceutical, Irvine, CA, USA) vials will be reconstituted with 0.9 % NaCl bacteriostatic solution by adding 2 ml to 100 units of lyophilized toxin. A 1cc syringe with a 30-gauge 1/2-inch needle will be used to administer at each site (1 syringe- needle for each side). Two units of BTX-A will be administered at each injection site. There will be 5 injection sites per side of forehead, for a total of 10 injection sites (20 units) for each participant. All injections will remain at least 2 cm from the superior orbital rim to reduce the potential of brow and eyelid ptosis.

If there is toxin remaining in the vial, this will be stored/refrigerated until needed again. Before it is used, the cap will be cleaned off with an alcohol swab. If an open, reconstituted vial is not used after 48-72 hours, the toxin will be discarded (13).

Participant perception of pain at the injection site will be evaluated by asking them to rate their pain, on a scale 0-10 for each side of the forehead (see Appendix 1).

## **SCHEDULED STUDY VISITS AND ASSESSMENTS**

### **Baseline Visit**

After reviewing and signing the informed consent form, all potential participants will undergo a baseline evaluation in order to determine study eligibility, establish baseline ocular characteristics and determine randomization group based on the computer-generated assignment. Participant demographics including age, gender, and race will be recorded as well as medical and medication history which will include previous use of botulinum toxin and if so the location of the injection and the date.

## Scheduled Follow-up Visits

Participants will follow-up 2 weeks (+/- 3 days), 6 weeks (+/- 2 weeks) and 16 weeks (+/- 2 weeks) after the injection.

Table 1. Time Windows for Scheduled Follow-up Visits (number of days after injections)

Follow-Up Visit	Ideal Follow-up Time	Visit Window
Week 2	14 days	11 days – 17 days
Week 6	42 days	35 days – 49 days
Week 16	112 days	98 days – 126 days

## Scheduled Assessments

Table 2 outlines the schedule of assessments at each visit throughout the study period.

Table 2: Schedule of Assessments

Assessment	Baseline	Injection	Week 2	Week 6	Week 16
Informed Consent	X				
Demographics	X				
Medical/Ophthalmic History	X				
Medication History	X		X	X	X
Inclusion/Exclusion Criteria	X				
Exophthalmometry	X		X	X	X
Bilateral Brow Excursion	X		X	X	X
External Photography-relaxed neutral expression	X		X	X	X
External Photography-maximal brow elevation	X		X	X	X
Injection		X			
Satisfaction Survey			X	X	X

Universal Pain Scale		X			
Randomization	X				
Adverse Events		X	X	X	X

### **Assessments**

The same examiner should perform the same assessments for each participant.

### **Medications**

All current patient medications, including vitamins and supplements should be documented and reviewed, to assess for any medication that may affect neuromuscular function at all study visit.

### **Exophthalmometry**

The distance between both lateral canthi will be measured using a Hertel exophthalmometer (mm) at Baseline, Week 2, Week 6 and Week 16 Visits.

### **Brow Excursion**

Brow excursion will be assessed at Baseline, Week 2, Week 6 and Week 16. Visits. Examinations will be performed by a masked examiner. Eyebrow excursion will be measured by using a purple marking pen and placing a mark just above the brow, parallel to the center of the pupil while the participants is in a relaxed neutral expression. Then, the participant will then be asked to raise the brows and the excursion of the brow from resting position to maximum elevation will be measured in millimeters.

### **External Photography**

Patients will be photographed at Baseline, Week 2, Week 6, and Week 16 Visits. Photos will be taken using the same digital camera. Patients will be photographed in both a relaxed, neutral expression, and while exhibiting maximal voluntary eyebrow elevation. All photos will be transferred to Adobe Photoshop (Adobe Systems, INC).

The method described previously by Gordin EA et al. (8) will be used to assess eyebrow height. The lateral intercanthal distance will be measured to standardize the photos by drawing a horizontal line from one lateral canthus to the other. Baseline brow height will be obtained measuring the distance between the line and a point taken at the superior-most aspect of the eyebrow, positioned directly above the mid-pupillary axis.

Measurements will be made at 150% magnification, viewing images on and Mac OS High Sierra Version 10.13.3 with a 15-in display and a screen resolution of 1920 x 1200 pixels. The lateral intercanthal distance will be used to normalize the brow height from each photograph to account for any differences in the camera-to-patient distance. For each patient, the ratio brow height to intercanthal distance will be calculated. Then the ratio obtained during the neutral brow position will be subtracted from that measure during active brow elevation for both sides (pretreatment with anesthetic and petrolatum) to yield brow elevation. This will be calculated for each picture taken at the baseline visit and at each follow up visit.

### **Participant Appearance Satisfaction Survey**

Participant satisfaction survey will be conducted at Week 2, Week 6 and Week 16 Visits. The survey will include questions about the overall appearance of their forehead for each side and will be recorded using a 5-point rating scale: 4 = very satisfied, 3 = satisfied, 2 = neutral, 1 = dissatisfied and 0 = very dissatisfied. Participants will also be asked if there is a noticeable difference between the 2 sides of their face.

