### **Background:**

Botulinum toxin type A (BTX-A) is a potent neurotoxin that blocks the presynaptic acetylcholine release at the neuromuscular junction, causing a dose-dependent weakness or paralysis of skeletal muscle. Recovery of muscle function occurs through proximal axonal sprouting and muscle re-innervation by formation of a new neuromuscular junction. Botulinum toxins are currently used for the treatment of a variety of medical disorders including spastic facial conditions (essential blepharospasms, hemifacial spasms), strabismus, sphincter dysfunction, hyperlacrimation, hyperhidrosis and headaches (1-4). In addition, botulinum toxin has been used in the treatment of facial rhytides such as crow's feet, and glabellar lines with great aesthetic results (5, 6). More recently, the US Food and Drug Administration approved the use of Botox for the temporary improvement in the appearance of moderate to severe forehead lines associated with frontalis muscle activity in adults.

A number of factors have been postulated that may affect the efficacy and duration of action of botulinum toxin type A including reconstitution process, dilution (units per volume), storage time after reconstitution and depth of administration (7,8). The use of topical anesthetic prior to administration of BTX-A for the treatment of facial cosmetic rhytides and blepharospasm has been proposed to have a deleterious impact on BTX-A effect, but the data is very limited (7). Multiple studies have investigated the use of

topical vibration, topical ice, vapocoolants and topical anesthesia as methods to decrease the pain associated with the injection of BTX-A (9-12) without decreasing the efficacy of BTX-A. However, there is no consensus on standard of care for administration of anesthesia prior to BTX-A administration. While many surgeons use one or a combination of the anesthetizing methods above to decrease pain associated with the injection, others use none.

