## **OBJECTIVES**

The objective of this study is to determine whether there is a difference in clinical effect (weakness/paralysis of the frontalis muscle), duration of effect, level of discomfort and patient satisfaction in patients receiving topical anesthesia (2.5% lidocaine/2.5 % prilocaine cream, Impax Laboratories, LLC) on one side of the forehead and petrolatum ointment on the other prior to BTX-A administration for the treatment of forehead rhytides.

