## **Outcome Variables**

- Primary outcome variable is change of eyebrow excursion on each side of the forehead from baseline to each follow-up visit.
  
- Secondary outcome variables
  - Duration of effect, defined as the elapsed time from injection to the end of botulinum, such that return of baseline frontalis function, i.e. within 2 mm of baseline value
  - Perception of pain immediately after injection at each side
  - Patient satisfaction for each side
  - Patient's perception of difference in efficacy

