### **Data Analysis**

Data will be summarized by mean (SD) and compared for continuous variables, e.g. age, eyebrow excursion, etc., and frequency (%) for discrete variables, e.g. sex, end of effect at each follow up, etc. Eyebrow excursion and patient satisfaction at each follow up as well as duration of effect and pain score will be compared between the topical anesthetic pretreated and non-pretreatment groups using paired t-test; while percent of end of effect at each follow-up visit, rate of complications and subjective pain will be compared using McNemar test.

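### The item behind perceived difference in efficacy is not specified to record which side, so a noticed difference cannot be attributed to anesthetic or petrolatum

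*Combined protocol and SAP*

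**What the plan says.** Outcome Variables lists "Patient's perception of difference in efficacy" as the last secondary outcome. It gives no definition, scale, direction or time point. "Patient satisfaction for each side" is a separate entry in the same list.

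The section Participant Appearance Satisfaction Survey describes two kinds of item, both collected at Weeks 2, 6 and 16:

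- A rating by side: "The survey will include questions about the overall appearance of their forehead for each side", scored from 0 to 4.
- A comparison: "Participants will also be asked if there is a noticeable difference between the 2 sides of their face".

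The comparison is the only item in the document that asks participants to set one side against the other. Nothing is said about recording which side, or how large the difference is. The survey form is not reproduced; the one appendix is the pain tool.

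Data Analysis states that "Eyebrow excursion and patient satisfaction at each follow up as well as duration of effect and pain score will be compared" by paired t-test. It assigns the McNemar test to end of effect, complications and subjective pain. Perceived difference is named in neither list. A general statement that discrete variables are summarized by frequency and percent would cover it descriptively.

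**The concern.** The scientific worry behind the trial has a direction. The Background says that topical anesthetic before the toxin "has been proposed to have a deleterious impact on BTX-A effect". A participant who sees a difference because the anesthetic side is weaker gives the same answer as one who sees the petrolatum side as weaker, and the protocol describes nothing that separates the two.

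A yes need not come from treatment at all. The exclusion criteria remove only brow asymmetry above 5 mm, and Table 2 schedules no survey at baseline. A participant whose brows differed before injection may report a difference at every visit, and there is no baseline answer to set against it.

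At stake is the participant's own comparative judgement of efficacy. If the side is not asked at the visit, it cannot be reliably recovered later.

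**Working it through.** **The plan's own figure.** The documents give no number for this outcome. The only sample size is the 14 participants for brow excursion. It follows from the two-sided paired normal approximation with SD 2.31 mm, difference 2 mm, 5% significance and 90% power: n = ((1.960 + 1.282) × 2.31 / 2)² = 14.02. That figure is used here only as the number of people who can answer the survey.

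**What the item can yield.** Side is randomized within each person (Randomization), so a left or right answer could be decoded to anesthetic or petrolatum. As described, the item gives one answer per participant per visit, with no answer for each side. The paired t-test and the McNemar test both need a response from each side, so neither planned test could be carried over to it. What remains is a count of yes answers out of those surveyed.

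**What the count hides.** Suppose k of 14 participants say yes, and a of those k see the stronger effect on the petrolatum side. The item records k, not a. If a were recorded, the two-sided exact binomial (sign) test with null probability 0.5 would apply. When all k point the same way, p = 2 × (1/2)^k. When the split is even, p = 1.00.

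| Yes answers, k (assumed) | Recorded by the item | All one way, either direction | Even split |
|---|---|---|---|
| 4 | 4/14 | 2/16 = 0.125 | 1.00 |
| 6 | 6/14 | 2/64 = 0.031 | 1.00 |
| 8 | 8/14 (57%) | 2/256 = 0.008 | 1.00 |
| 14 | 14/14 | 2/16384 = 0.0001 | 1.00 |

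The documents give no expected rate of yes answers, so k is an assumption throughout. With k = 8, the recorded 8/14 fits 8:0, 4:4 and 0:8 equally well.

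**What recording the side would allow.**

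- With 5 all one way, p = 2/32 = 0.0625; with 6, p = 0.031. At least 6 participants who notice a difference, all in the same direction, are therefore needed for p ≤ 0.05.
- 9 of 10 in one direction gives 2 × (10 + 1)/1024 = 0.021.
- 12 of 14 gives 2 × (91 + 14 + 1)/16384 = 0.013.
- 11 of 14 gives 2 × (364 + 91 + 14 + 1)/16384 = 0.057.

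**Pre-existing asymmetry.** If each side is equally likely to be assigned the anesthetic and the pretreatment makes no difference, asymmetry present before treatment favors either pretreatment equally often. The null probability of 0.5 then still holds. Asymmetry adds noise to a directional answer but does not bias the test. The undirected count has no such protection, because there is no reference rate for it.

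**The case against.** The strongest reply is that the item does what the outcome says. The stated objective is to "determine whether there is a difference in clinical effect (weakness/paralysis of the frontalis muscle), duration of effect, level of discomfort and patient satisfaction", which is non-directional and does not list perceived difference in efficacy. The outcome is itself worded as a perception of difference. The share of participants who can see any difference is a legitimate descriptive result, and the frequency-and-percent rule in Data Analysis covers it. This stands. A reader might infer that the item is worthless or that the trial's question goes unanswered; the documents do not support either reading.

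Second, direction is available elsewhere. Masked brow excursion, the photographs, duration of effect and the 0 to 4 satisfaction ratings are all side-specific, and the ratings come from the same survey at the same visit. This also stands, and it confines the point to one secondary outcome. The ratings are only a partial substitute. They measure satisfaction with appearance, which the protocol lists as a separate outcome, and a participant can rate both sides equally while seeing one as weaker. The documents give no basis for saying how often that would happen.

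Third, the survey form is not in the documents, so it may already ask which side. A reader might infer that direction is definitely not collected; that cannot be concluded. What can be said is that the protocol does not specify it and names no comparison that would use it.

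The reference to the face rather than the forehead carries little weight alone, since the preceding sentence of the survey section concerns the forehead and only the forehead is injected.

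**Conclusion.** The point holds in a limited form. As the protocol describes it, the item supports a descriptive share of participants who notice a difference. It does not support attributing that difference to anesthetic or petrolatum, and asymmetry of up to 5 mm at entry can contribute to a yes.

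One secondary outcome is affected. The primary outcome, duration, pain and per-side satisfaction are untouched, and no stated figure is overturned. The illustration with 8 yes answers rests on an assumed count. The conclusion rests on the survey section being a complete description of the item; if the form already records the side, what remains is to say so and to name the analysis. The change is worth making because it is nearly free and must be in place before the answers are collected.

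**What to change.** In Participant Appearance Satisfaction Survey, specify the item as two steps: *Is there a noticeable difference in effect between the two sides of your forehead? If yes, which side shows the stronger effect: left or right?* State that left and right are decoded to pretreatment only after data lock. If the form already asks this, describe it in the protocol.

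In Data Analysis, add that, separately at Weeks 2, 6 and 16, the share favoring each pretreatment among those who notice a difference will be compared by exact binomial (sign) test, and the share reporting no difference will be given. Name one of the three visits in advance as the main one, so that the result does not depend on choosing among three tests afterwards.

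The cost is one extra survey question per visit and a short addition to the analysis text. The test will have low power: fewer than 6 participants noticing a difference cannot give p ≤ 0.05, so the split should be reported as counts whatever the p-value.

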### **Universal Pain Scale Assessment**

Participant pain and/or discomfort will be assessed on the day of Injection (post injection) (Appendix 1) for each side.

### **ADVERSE EVENTS**

An adverse event (AE) is any untoward medical occurrence in a participant who is administered a test article. The AE does not necessarily have a causal relationship with the treatment. An AE can therefore be any unfavorable and unintended sign (including

an abnormal laboratory finding), symptom, or disease temporally associated with study treatments.

A non-serious AE is defined as a change in a participant's ophthalmic and/or medical health that is not life-threatening, does not require hospitalization, does not prolong a current hospitalization and is not disabling. All AEs must be reported whether they are considered study-related or not.

### **Serious Adverse Events**

A serious adverse event is defined as any adverse experience occurring at any time during the study that results in:

- Death
- Life-threatening
- Inpatient hospitalization
- Prolongation of existing hospitalization
- Disability or permanent damage (including vision threatening complications)
- A congenital anomaly/birth defect
- Required intervention to prevent permanent impairment or damage and/or other serious important medical events

All SAEs will be submitted to the IRB pursuant to their IRB policy.

### **Recording Instructions**

Mild, moderate, or severe should be used to describe the maximum intensity of the adverse event.

- Mild – Does not interfere with the participant's usual functions
- Moderate – Interferes to some extent with the participant's usual functions
- Severe – Interferes significantly with the participant's usual functions

It should be noted that a severe intensity does not necessarily mean it is an SAE.

The investigator will also be asked to determine the likelihood of the relationship between the study intervention and the AE.

### **Follow-up of Adverse Events**

For participants who have ongoing ocular adverse events at the time of their last follow-up visit, it is recommended that the Investigator schedule a follow-up visit to determine the outcome of the event.

### **Safety Considerations**

At any point in the study, or after the study has concluded, a subject can return for examination if needed. An on-call ophthalmologist will be available at all times, and subjects will be given emergency contact information.

### **Data Analysis**

Data will be summarized by mean (SD) and compared for continuous variables, e.g. age, eyebrow excursion, etc., and frequency (%) for discrete variables, e.g. sex, end of effect at each follow up, etc. Eyebrow excursion and patient satisfaction at each follow up as well as duration of effect and pain score will be compared between the topical anesthetic pretreated and non-pretreatment groups using paired t-test; while percent of end of effect at each follow-up visit, rate of complications and subjective pain will be compared using McNemar test.

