**NCT03799484**

**Version Date:** 11/30/2018

**Title:** Randomized, Single Center, Masked Study Comparing the Efficacy of Botulinum Toxin Type A Injection After Topical Anesthesia versus Petrolatum Ointment

**Principal Investigator:** [name]

**Biostatistician:** [name]

**Study Coordinator:** [name], BS

**Population:** Sample size ~14, male/female, 18 – 65 years of age, diagnosed with forehead rhytides electing for treatment with botulinum toxin Type A

**Number of sites:** 1, Robert Cizik Eye Center

**Study Duration:** Patient participation time will be approximately 16 weeks

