### **Exclusion criteria**

Patients who meet the following exclusion criteria may NOT be enrolled

- Previous injection of botulinum toxin in the intended treatment area for the study within the last 4 months
- Known allergy to botulinum toxin
- Known history of sensitivity to local anesthetics of the amide type
- Existing disorder of neuromuscular transmission (e.g. Myasthenia gravis or Lambert-Eaton syndrome)
- Usage of medication with effect on neuromuscular function
- Women of childbearing potential (who are not postmenopausal for at least 1 year or surgically sterile), who are pregnant or nursing or intend to become pregnant during the time of the study
- Significant brow asymmetry ( $> 5$ mm)
- Unable to follow-up for the duration of the study (16 weeks)

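### Duration of effect is compared by paired t-test, but return is seen only at Weeks 2, 6 and 16 and no value is set for a side not returned by Week 16

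*Combined protocol and SAP*

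**What the plan says.** Outcome Variables lists first among the secondary outcomes: "Duration of effect, defined as the elapsed time from injection to the end of botulinum, such that return of baseline frontalis function". The same line puts the threshold at 2 mm from the baseline value.

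The looks are few. Scheduled Follow-up Visits: "Participants will follow-up 2 weeks (+/- 3 days), 6 weeks (+/- 2 weeks) and 16 weeks (+/- 2 weeks) after the injection". Brow Excursion: "Brow excursion will be assessed at Baseline, Week 2, Week 6 and Week 16. Visits". Table 2 agrees, and the photographs follow the same schedule, so they add no time points. The title page states: "Patient participation time will be approximately 16 weeks". No later measurement is planned.

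Data Analysis applies the paired t-test to duration: excursion and satisfaction at each follow-up, "as well as duration of effect and pain score will be compared between the topical anesthetic pretreated and non-pretreatment groups using paired t-test". It also plans a comparison that needs no duration value: "percent of end of effect at each follow-up visit, rate of complications and subjective pain will be compared using McNemar test".

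No section says what duration an unreturned side receives, whether its pair is dropped, or which date between two visits counts as the return.

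**The concern.** The exact time of return is never observed. It is known only to lie between two visits or, for a side still weak at the last visit, after that visit. A paired t-test needs one number per side, so someone must choose it, and the plan leaves that choice open.

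The split-face design sharpens the problem. Both sides are examined at the same visits, so a pair can show a difference only if its sides fall in different intervals or an unreturned side gets a value later than its last visit. Scoring an unreturned side at the last visit is the natural default. It turns every pair that is discordant at Week 16 into an exact zero.

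Duration is part of the stated objective. The same data could yield no testable difference or a significant one, with a size in weeks set by an unwritten rule that might be chosen after the assignments are known.

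**Working it through.** **The plan's own figure.** The documents give a sample size only for excursion. With 2.31 mm as the SD of the paired difference, n = (2.31 × (1.960 + 1.282) / 2)² = 14.02, which reproduces the stated 14. There is no sample size, expected duration or SD for duration of effect.

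**Gap between the last two looks (Table 1).** The shortest is 98 − 49 = 49 days and the longest 126 − 35 = 91 days. The text gives Week 6 a window of ± 2 weeks (28 to 56 days), which would make the gap 42 to 98 days. Text and table need reconciling.

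**Effect of the code, first example.** The pattern is assumed: 14 pairs, 5 with one side back at Week 16 and the other not (always the same arm), and 9 with both sides in the same interval. Let c be the code in weeks for an unreturned side.

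- c = 16, or these pairs dropped: every difference is 0 and no test is possible.
- c > 16: mean difference = 5(c − 16)/14. SD = (c − 16) × √[(5 − 25/14)/13] = 0.497(c − 16). So t = 0.357 / (0.497/√14) = 2.69 on 13 df, p = 0.019. The factor (c − 16) cancels from t but not from the mean.

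| Code c | Mean difference (weeks) | p |
|---|---|---|
| 16 or dropped | 0 | no test |
| 17 | 0.36 | 0.019 |
| 18 | 0.71 | 0.019 |
| 20 | 1.43 | 0.019 |
| 24 | 2.86 | 0.019 |

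**Second example, with earlier discordance as well.** Take 3 pairs at 6 vs 16, 4 pairs both at 16, 3 pairs both unreturned, and 4 pairs at 16 vs unreturned. The mean difference is (3 × 10 + 4(c − 16))/14. It is 2.14 weeks at c = 16 (p = 0.082), 2.43 at 17 (p = 0.046), 3.29 at 20 (p = 0.0095) and 4.43 at 24 (p = 0.0035). Dropping pairs with an unreturned side leaves 7 pairs and p = 0.078. Here the code also moves the p-value.

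**Power.** Assumed inputs: n = 14, normal true durations with SD 2.5 weeks, between-side correlation 0.6, two-sided 5%, 20,000 simulated trials per row. Each duration is recorded at the first visit at or after return.

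| True means (weeks) | t-test, coded 16 | t-test, coded 20 | t-test on scores 1–4 | Exact sign test | Best single-visit exact McNemar |
|---|---|---|---|---|---|
| 12 vs 14 | 0% | 18% | 20% | 2% | 2% |
| 10 vs 14 | 0.6% | 37% | 50% | 12% | 5% |
| 6 vs 10 | 91% | 92% | 91% | 71% | 64% |
| 14 vs 18 | 0% | 97% | 97% | 90% | 89% |

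For 14 vs 18 the recorded mean difference runs from 0.01 weeks (coded 16) to 4.6 weeks (coded 24) for a true 4.0. For 6 vs 10, where returns straddle Week 6, it is 4.7 for a true 4.0.

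Other assumptions give the same pattern. With SD 3.5, 14 vs 18 gives 0% coded 16 and 81% coded 20. With SD 4, correlation 0.7 and means of 12 vs 16, power is 0.8% coded 16, 51% coded 18, 72% coded 20 and 79% coded 24.

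**Type I error.** With equal true durations, the week-coded t-test rejected in 0 to 4.9% of trials and the t-test on scores in no more than about 5%.

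**The case against.** The strongest reply is that the plan lacks one sentence on an unpowered secondary outcome, and that the visit-wise McNemar tests already compare the sides without any code. Much of this stands. At 14 vs 18 weeks, McNemar at Week 16 has 89% power. It does not estimate duration, though, and it is weak when discordance is spread over visits (5% for 10 vs 14, against 50% for the scores).

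Three stronger readings are tempting, and the documents do not support them.

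- A reader might infer that detection moves freely with the code. It does not. The main divide is between scoring at the last visit (or dropping the pair) and any later value. Among later values the p-value is constant in the first example and moves only when earlier visits are also discordant. At 6 vs 10 weeks the code hardly matters.
- A reader might infer that many sides will be unreturned at Week 16. The exclusion of "Previous injection of botulinum toxin in the intended treatment area for the study within the last 4 months" covers a period longer than 16 weeks (4 months is about 17.4 weeks), but it is a rule on prior treatment, not an expected duration. The endpoint is return to within 2 mm, not full recovery, and the Week 16 window runs to day 126, or 18 weeks. Unreturned sides are plausible, not shown.
- A reader might infer that the t-test must give way to a sign test. That would lose power needlessly (71% against 91% for 6 vs 10). With 5 untied pairs, all in one direction, it gives p = 0.0625; at least 6 are needed for p = 0.031.

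**Conclusion.** The point holds as a gap in the analysis of duration that should be closed before unmasking. It is more than missing detail: a mean of visit-coded, censored times does not measure duration, and the most natural coding discards the pairs that carry the information around Week 16.

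If no side is unreturned at Week 16, the code is irrelevant and only the coarseness of the visits remains. If some are, power for a difference around Week 16 can go from about 97% to 0% with the rule chosen, and the reported size scales with the code. These powers rest on assumed means, SDs and correlations; the examples rest on assumed patterns of discordance. The structural part rests on the documents alone: shared visits, a last look at about 16 weeks, and no rule.

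The harm is to power and to the estimate. Nothing here suggests excess false positives.

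**What to change.** In Data Analysis, replace duration in weeks by an ordered score for each side. Use the first post-injection visit at which excursion is within 2 mm of that side's baseline: 1 = by Week 2, 2 = Weeks 2–6, 3 = Weeks 6–16, 4 = not by Week 16. State that category 4 is never set equal to a Week 16 return. Then:

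- Compare sides by paired t-test on the scores, with an exact sign test as sensitivity analysis.
- Where a visit is missed, merge the adjoining intervals for both sides of that patient, and state the score of a merged interval (for example, the average of the scores it replaces).
- Report counts per interval by side, and the McNemar result per visit. Count separately any side that never moved more than 2 mm from baseline, since it would score 1.
- Do not report a mean difference in weeks from coded times.

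The cost is a change of wording and a little programming on data already collected, with no extra visits. The result becomes an ordered comparison, not a difference in weeks. Equal spacing of the scores is a convention: for sides in categories 2 to 4 it gives the same t as coding them 6, 16 and 26 weeks, which is why it must be fixed in advance. Differences that lie wholly within the gap between Weeks 6 and 16 stay unseen under any analysis.
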